6.2.2.2. Laboratory data

Missing laboratory results (including immunological data) will not be replaced.

6.2.2.3. Daily recording of solicited events

An eDiary will be used in this study to capture solicited administration site or systemic events, the following rules are applicable for all solicited events except fever:

- Denominators for the summary of administration site (or systemic) solicited events will be calculated using the number of participants who respond to one of the three questions below:

- The question concerning the occurrence for the **Redness and Swelling** symptoms (i.e., is there any Swelling/Redness at the administration site?).
- The question related to the intensity (i.e.,; Please indicate the intensity of the <symptom>)
- The question related to medically attention (i.e.,; Was advice taken for a healthcare professional for this event?).

For the **Redness and Swelling** symptoms the following rules will also be applied:

- When a participant answer “No” to the question: is there any Swelling/Redness at the administration site? the daily measurements will be imputed as None.
- When a participant answer “Yes” to the question: is there any Swelling/Redness at the administration site? any missing daily recordings will be given imputed values to allow them to contribute to the ‘Any’ rows but not to specific grade rows of the solicited event summary tables.

The following table shows how participants contribute to each category for a specific solicited event over the Day X to Day Y post-dose period:

Solicited event category	Participants included in the calculation of the numerator
Any	All participants with at least one occurrence of the adverse event at Grade 1, Grade 2, or Grade 3 between Day X and Day Y or with the adverse event marked as present and at least one missing daily recording between Day X and Day Y
At least Grade 1	All participants with at least one occurrence of the adverse event at Grade 1, Grade 2, or Grade 3 between Day X and Day Y
At least Grade 2	All participants with at least one occurrence of the adverse event at Grade 2 or Grade 3 between Day X and Day Y
At least Grade 3	All participants with at least one occurrence of the adverse event at Grade 3 between Day X and Day Y

For fever, the summary tables will not include the row ‘Any’. The missing daily records do not contribute to the number participants reporting fever by half degree (°C): ≥ 38 ; ≥ 38.5 , ≥ 39 , ≥ 39.5 and ≥ 40 .

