
 To evaluate the safety and reactogenicity following administration of the RSVPreF3 OA investigational vaccine and the FLU vaccine, co-administered or administered alone. 	
 Percentage of participants reporting each solicited event with onset within 7 days after vaccine administration (i.e., the day of vaccination and 6 subsequent days). Percentage of participants reporting unsolicited AEs (pIMD, non-serious AE or serious AE) within 30 days after vaccine administration (i.e., the day of vaccination and 29 subsequent days). Percentage of participants reporting SAEs after vaccine administration (Day 1) up to study end (6 months after last vaccination). Percentage of participants reporting pIMDs after vaccine administration (Day 1) up to study end (6 months after last vaccination).

CCI

FLU vaccine refers to FLU aQIV

AE = adverse event; CCI = ; GMT = geometric mean titer; HI = hemagglutination inhibition; MGI = mean geometric increase; RSVPreF3 OA = respiratory syncytial virus PreFusion protein 3 older adult; SAE = serious adverse event; SCR = seroconversion rate; SPR = seroprotection rate; pIMD = potential immune-mediated disease; SCR = percentage of vaccinees who have either a HI pre-dose titer $< 1:10$ and a post-dose titer $\geq 1:40$ or a pre-dose titer $\geq 1:10$ and at least a 4-fold increase in post-dose titer.

SPR = percentage of vaccinees with a serum HI titer $\geq 1:40$ that usually is accepted as indicating protection.

[figure not shown]
MGI = geometric mean of the within-participant ratios of the post-dose titer over the pre-dose titer.

Details related to attributes of estimands covering intercurrent events, population and treatment definition are provided in Section 9.

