10.3.8. Assessment of intensity and toxicity

10.3.8.1. Assessment of intensity

The intensity of the following solicited AEs will be assessed as described:

Table 26 Intensity scales for solicited events (Amended: 13 December 2022)

Event	Intensity grade	Parameter
Pain at administration site	0	None
	1	Mild: Any pain neither interfering with nor preventing normal everyday activities.
	2	Moderate: Painful when limb is moved and interferes with everyday activities.
	3	Severe: Significant pain at rest. Prevents normal everyday activities.
Redness at administration site		Greatest surface diameter in mm
Swelling at administration site		Greatest surface diameter in mm
Temperature*		Temperature in °C
Headache	0	None
	1	Mild: Headache that is easily tolerated
	2	Moderate: Headache that interferes with normal activity
	3	Severe: Headache that prevents normal activity
Fatigue	0	None
	1	Mild: Fatigue that is easily tolerated
	2	Moderate: Fatigue that interferes with normal activity
	3	Severe: Fatigue that prevents normal activity
Myalgia	0	None
	1	Mild: Myalgia present but does not interfere with activity
	2	Moderate: Myalgia that interferes with normal activity
	3	Severe: Myalgia that prevents normal activity
Arthralgia	0	None
	1	Mild: Arthralgia present but does not interfere with activity
	2	Moderate: Arthralgia that interferes with normal activity
	3	Severe: Arthralgia that prevents normal activity

*Refer to the Section 1.3 (SoA) for the definition of fever and the preferred location for temperature measurement.

The maximum intensity of local injection site erythema/swelling and fever will be scored at GSK as follows:

	Erythema/swelling	Fever
0:	≤ 20 mm	< 38.0°C
1:	> 20 - ≤ 50 mm	≥ 38.0°C - ≤ 38.5°C
2:	> 50 - ≤ 100 mm	> 38.5°C - ≤ 39.0°C
3:	> 100 mm	> 39.0°C

The investigator will assess the maximum intensity that occurred over the duration of the event for all unsolicited AEs (including SAEs) recorded during the study. The assessment will be based on the investigator's clinical judgment.

The intensity should be assigned to 1 of the following categories:

1 (mild)	= An AE which is easily tolerated by the participant, causing minimal discomfort and not interfering with everyday activities.
2 (moderate)	= An AE which is sufficiently discomforting to interfere with normal everyday activities.

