6.2.3.7. Duration of events

For the duration of solicited AEs:

- The duration of the event will be calculated as the sum of the individual days with the event reported as Grade 1 or higher or reported as missing during the solicited event period (see Section 6.2.2.3 for missing data). For Grade 3, the duration will be calculated as the sum of individual days with the event reported as Grade 3 or reported as missing during the solicited event period.

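### SAP 6.2.2.3, read literally, lets a missing diary day put redness or swelling of 20 mm or less (Grade 0) into the 'Any' row, while the same measurements in a complete diary stay out

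*SAP*

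**What the plan says.** Protocol 10.3.8.1 sets the size grades under the statement "The maximum intensity of local injection site erythema/swelling and fever will be scored at GSK as follows". Erythema or swelling of 20 mm or less is Grade 0, above 20 to 50 mm Grade 1, above 50 to 100 mm Grade 2, and above 100 mm Grade 3. SAP Table 5 repeats these cut-offs.

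SAP 6.2.2.3 bases redness and swelling on a presence question without a size limit: "is there any Swelling/Redness at the administration site". After a 'No', the daily measurements are set to none. After a 'Yes', "any missing daily recordings will be given imputed values to allow them to contribute to the" 'Any' rows, but not to the rows for specific grades.

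The numerator table in the same section defines 'Any' by two conditions joined by 'or':

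- "at least one occurrence of the adverse event at Grade 1, Grade 2, or Grade 3" in the window; or
- "with the adverse event marked as present and at least one missing daily recording between Day X and Day Y".

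'At least Grade 1' uses the first condition only. For fever the section takes the other course: "The missing daily records do not contribute to the number participants reporting fever by half degree".

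The endpoint served is secondary (Protocol Section 3): "Percentage of participants reporting each solicited event with onset within 7 days after vaccine administration". SAP 4.3.2 tabulates any-grade percentages after each dose and overall, and repeats them by age group.

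**The concern.** For pain and the graded systemic symptoms, Grade 0 means none, so an event marked present cannot be Grade 0. For redness and swelling it can, because a lesion of 1 to 20 mm is both present and Grade 0. The second condition for 'Any' does not look at the recorded diameters, so for these participants a gap in the diary decides whether they are counted.

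The row then matches neither natural definition. It is not everyone who reported redness or swelling, because complete diaries with small lesions are left out. It is not everyone above 20 mm, because incomplete diaries with small lesions are let in. At stake is the meaning of two percentages in the reactogenicity tables, which would move with diary compliance as well as with reactogenicity.

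**Working it through.** The plan gives no figure to reproduce: neither the frequency of small reactions nor the rate of missing diary days is stated.

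**Step 1. Apply the rule.** Inputs are the two conditions in SAP 6.2.2.3, the cut-offs in Protocol 10.3.8.1 and a 7-day window. Diameters are in mm for Days 1 to 7, and '–' is a missing recording.

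| Presence answer | Diary | 'Any' | 'At least Grade 1' |
|---|---|---|---|
| Yes | 20, 15, 10, 5, 0, 0, 0 | no | no |
| Yes | 20, 15, 10, 5, –, 0, 0 | **yes** | no |
| Yes | 20, –, 10, 5, 0, 0, 0 | **yes** | no |
| Yes | 5, 0, 0, 0, 0, 0, – | **yes** | no |
| No | 0, 0, 0, 0, 0, 0, – | no | no |
| Yes | 25, 10, 0, 0, 0, 0, 0 | yes | yes |

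Rows 1 and 2 have the same recorded lesion and differ only in one missing day. No other section of either document adds a diameter condition.

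**Step 2. Size, on assumed inputs.** Let q be the share of participants who answer 'Yes' and whose true diameters are all 20 mm or less, and m the share of diary days missing, with days missing independently of each other and of the reaction. Then

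- P(at least one missing day in 7) = 1 − (1 − m)^7
- rise in 'Any', relative to a count of lesions above 20 mm, = q × [1 − (1 − m)^7]

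| m | P(at least one missing) | q = 2% | q = 5% | q = 10% | q = 15% |
|---|---|---|---|---|---|
| 1% | 1 − 0.99^7 = 6.8% | 0.14 | 0.34 | 0.68 | 1.02 |
| 2% | 1 − 0.98^7 = 13.2% | 0.26 | 0.66 | 1.32 | 1.98 |
| 5% | 1 − 0.95^7 = 30.2% | 0.60 | 1.51 | 3.02 | 4.53 |

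Entries are percentage points per diary period. With 514 participants per group, the extremes are about 1 participant (0.0014 × 514 = 0.7) and 23 participants (0.0453 × 514 = 23.3).

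**Step 3. Does it bias the group comparison?** Control has two 7-day diary periods with one injection each. Co-Ad has one period with two injections, one in each arm (Protocol Table 7), and SAP 6.2.3.9 collapses the sites to one occurrence. Take q = 5-15% per injection, m = 2-5%, and independent reactions:

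- Co-Ad: (1 − 0.95²) × 0.132 = 1.3 points, to (1 − 0.85²) × 0.302 = 8.4 points.
- Control: 1 − (1 − 0.05 × 0.132)² = 1.3 points, to 1 − (1 − 0.15 × 0.302)² = 8.8 points.

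If instead the same people react at both injections, the upper case is 0.15 × 0.302 = 4.5 points for Co-Ad and 0.15 × (1 − 0.95^14) = 0.15 × 0.512 = 7.7 points for Control. The difference therefore runs from near zero to about 3 points, depending on a correlation that the documents do not give. These two-injection figures also do not remove participants already counted for a lesion above 20 mm at the other injection.

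**The case against.** The best defence is that this is deliberate conservative imputation in a safety table: the missing day might have been the peak. That stands where no diameter was recorded at all. It does not explain why recorded diameters are ignored when there is a gap and decisive when there is none.

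A second defence is that the presence question may be asked daily. A wholly skipped day would then carry no 'Yes', and the imputation sentence could be read as covering only days marked present without a measurement. The SAP does not say which is meant, so the result for a wholly skipped day rests on the literal wording of the numerator table, which does not require 'present' and 'missing' to fall on the same day. Under the narrower reading the effect shrinks but remains: 8 mm on Day 2 and a 'Yes' without a diameter on Day 3 still counts.

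Third, 'At least Grade 1' already gives a clean count above 20 mm, and diary compliance is tabulated. This limits the harm. However, the gap between that row and 'Any' mixes participants with no diameter at all and participants with small recorded diameters plus a missing day. SAP 4.3.2 also names only any-grade and Grade 3 for the individual-event tables.

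A reader might go further and call the extra counts false. The documents do not support that. Everyone counted this way reported the event, and Protocol 10.3.7.1 has solicited events recorded whatever their intensity. The defect is inconsistent classification, not invented events.

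**Conclusion.** The point holds as a minor defect of definition. On the literal text, identical measurements of 20 mm or less are in or out of 'Any' redness or swelling according to diary completeness. The inflation, relative to a threshold of 20 mm, is roughly 0.1-4.5 percentage points per diary period. This rests on assumed inputs: 2-15% of participants with only small reactions, and 1-5% of diary days missing independently. If missing days cluster within participants, the effect is smaller at the same daily rate.

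The graded rows are protected, the output is secondary and descriptive, and no hypothesis test or sample size changes. A reader might infer that Control is inflated more than Co-Ad because it has two diary periods. The documents do not establish this: Co-Ad has two injection sites in its single period, and on independent reactions the two groups nearly match.

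**What to change.** In SAP 6.2.2.3, for redness and swelling:

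1. Apply the missing-recording condition only when the event is marked present and no diameter was recorded in the period. Otherwise let the recorded diameters decide.
2. State whether the presence question is asked daily or once per period.
3. Add a separate row for participants marked present whose recorded diameters are all 20 mm or less, split into complete diary and at least one missing day. The conservative bound then stays visible, and a reader can recover either definition.

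The cost is a wording change and one split table row, with no new data. The downside is that 'Any' becomes slightly less conservative when the missing day could have been the peak. For example, 18 mm on Day 1, Day 2 missing and 15 mm on Day 3 would leave 'Any' and appear in the new row under missing days.

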6.2.3. Data derivation

6.2.3.1. Age at first dose in years

Age will be calculated as the number of years between the year of birth and the year of first vaccination.

6.2.3.2. Age category at vaccination

As only the year of birth will be collected in the eCRF, there might be some discrepancies between the age computed using standard derivation rules and the age category used in SBIR for the minimization.

Therefore, for the analysis by age, the age categories will be determined according to the information entered in SBIR (add name of variable in SDTM), except for “ ≥ 65 YOA” category which will be obtained using the derived age because this category is not used in SBIR for minimization.

6.2.3.3. Temperature

Temperatures will be presented in degrees Celsius ($^{\circ}\text{C}$). Temperatures reported in degrees Fahrenheit ($^{\circ}\text{F}$) will be converted as follows:

$$\text{Temperature (Celsius)} = ([\text{Temperature (Fahrenheit)} - 32] \times 5)/9$$

6.2.3.4. Numerical serology results

Numerical serology results will be derived from the content of IS.ISORRES in the SDTM dataset. For all the assays available for the study, the following derivation rules apply:

IS.ISORRES	Derived value
“NEG”, “-”, or “(-)”	cut-off/2
“POS”, “+”, or “(+)”	cut-off
“< value” and value is \leq assay cut-off	cut-off/2
“< value” and value is $>$ assay cut-off	value
“> value” and value is $<$ assay cut-off	cut-off/2
“> value” and value is \geq assay cut-off	value
“value” and value is $<$ cut-off	cut-off/2
“value” and value is \geq cut-off	Value
“value” and value is $>$ ULOQ	ULOQ
All other cases	missing

Note: The Reverse Cumulative Distribution curves (RCC) generated will not use the ULOQ values but the exact value if the exact value is greater than ULOQ.

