8.1.4. Immunological correlates of protection

No generally accepted immunological correlate of protection has been demonstrated for the antigens used in the RSVPreF3 OA investigational vaccine or the FLU vaccine.

Although there is no accepted correlate of protection against influenza, either seasonal or pandemic, the protective role of antibodies against hemagglutinin is well established [Rimmelzwaan, 2008; Cox, 2013]. The serum hemagglutination inhibition (HI) assay is commonly used to measure the humoral response to hemagglutinin. HI titers have been shown to correlate with protection from infection in human studies and titers of 1:40 or greater have been accepted as a surrogate marker of potential vaccine efficacy by regulators [Hannoun, 2004; EMEA, 1997; FDA, 2007].

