Starting with an initial dilution of 1:10, a dilution series (by a factor of 2) is prepared up to an end dilution of 1:10 240. The titration endpoint is taken as the highest dilution step that shows complete inhibition of hemagglutination. All assays are performed in triplicate, and the final titer corresponds to the GMT of the 3 values. The usual cut-off value is = 10 1/DIL.

CCI

10.3. Appendix 3: Adverse events – definitions and procedures for recording, evaluating, follow-up, and reporting

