4. STATISTICAL ANALYSES

4.1. General Considerations

4.1.1. General Methodology

95% CI for proportion will be based on exact Clopper-Pearson CI [[Clopper](#), 1934].

95% CI for group difference in proportion will be based on Miettinen and Nurminen CI [[Miettinen](#), 1985].

The group adjusted GMT ratio will be based on a back transformation of group contrast in an ANCOVA model applied to the logarithm-transformed titers.

Primary Analysis: The ANCOVA model will include the treatment group and age category (age at vaccination: 65-69, 70-79 or ≥ 80 years) as fixed effects and the pre-dose log-10 titer as regressors.

Sensitivity Analysis: The ANCOVA model will include the treatment group and age category (age at vaccination: 65-69, 70-79 or ≥ 80 years) as fixed effects, center as the random effect and the pre-dose log-10 titer as regressors.

95% CI for GMT and GMT ratio will be based on a back transformation of student CI for the mean and difference of means (for GMT ratio) respectively of log-transformation (i.e., $10^{\wedge}CI$).

4.1.2. Definition:

- For all endpoints:

The baseline value will be the latest pre-dose assessment with a non-missing value, including those from unscheduled visits. If time is not collected, Day 1 assessments are assumed to be taken prior to first dose and used as baseline.

MG1 (mean geometric increase): The geometric mean of the within participant ratios of the post-dose titer over the pre-dose titer.

- For the RSV antigens:

A seronegative participant will be defined as a participant whose antibody titer/concentration is below the cut-off value of the assay. A seropositive participant is a participant whose antibody titer/concentration is greater than or equal to the cut-off value of the assay.

- For the FLU antigens:

SCR (seroconversion rate): The percentage of vaccinees who have either a HI pre-dose titer $< 1:10$ and a post-dose titer $\geq 1:40$ or a pre-dose titer $\geq 1:10$ and at least a four-fold increase in post-dose titer.

HI SPR (seroprotection rate): The percentage of vaccinees with a serum HI titer $\geq 1:40$ that usually is accepted as indicating protection.

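### SAP 6.2.3.4 sets an HI result of `<40` to 40, so any such result would count as seroprotected, and as seroconverted from a pre-dose titer of 10 or less

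*SAP*

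**What the plan says.** SAP 6.2.3.4 opens its conversion table with a general scope: "For all the assays available for the study, the following derivation rules apply". For results reported as an upper bound, a bound at or below the cut-off becomes half the cut-off, while a bound above it falls under "< value” and value is $>$ assay cut-off value", so the derived value is the bound.

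For HI, Protocol 10.2 states "The usual cut-off value is = 10 1/DIL" and describes the dilutions as "Starting with an initial dilution of 1:10, a dilution series (by a factor of 2) is prepared up to an end dilution of" 1:10 240.

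SAP 4.1.2 defines SPR as "The percentage of vaccinees with a serum HI titer $\geq 1:40$ that usually is accepted as indicating protection". SCR needs either a pre-dose titer below 1:10 with a post-dose titer of at least 1:40, or a pre-dose titer of at least 1:10 with "at least a four-fold increase in post-dose titer". Protocol 8.1.4 explains the weight given to the threshold: "titers of 1:40 or greater have been accepted as a surrogate marker of potential vaccine efficacy by regulators".

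SAP 4.2.2 deals only with titers below the cut-off (half the cut-off) and above the ULOQ (set to the ULOQ). SAP 6.2.3.5 refers to the 6.2.3.4 table for GMT and GMC. Neither document gives a separate rule for classifying SPR or SCR.

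**The concern.** A titer reported as below 40 cannot be 40 or more. The row nevertheless gives it the one value at which the inclusive threshold is met, so a known non-responder would be tabulated as a responder.

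The derived values feed the within-group SPR, SCR and MGI tables, the CBER and CHMP checks (SAP 4.3.1.2), the 10% SCR comparison (SAP 4.3.1.1), and the outcome and pre-dose covariate of the primary ANCOVA (SAP 4.2.2). The within-group tables and the CBER and CHMP checks are the most exposed, because nothing there offsets the error.

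**Working it through.** **Plan's own figure.** No power or sample-size figure is in dispute. For the SCR comparison (462 per group, 10% margin, 50% in both groups, one-sided 2.5%), Φ(0.10/√(2×0.5×0.5/462) − 1.96) = Φ(3.04 − 1.96) = Φ(1.08) = 86.0%, against 86.1% stated.

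**Step 1: apply the row literally.** Inputs: cut-off 10 (Protocol 10.2), the 6.2.3.4 table, the SPR and SCR definitions (SAP 4.1.2).

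| Pre-dose | Post-dose | Derived pre, post | Status under the SAP | What the reported results show |
|---|---|---|---|---|
| `<10` | `<40` | 5, 40 | SPR yes, SCR yes | neither |
| 10 | `<40` | 10, 40 (4-fold) | SPR yes, SCR yes | neither |
| 20 | `<40` | 20, 40 (2-fold) | SPR yes, SCR no | neither |
| 20 | `<80` | 20, 80 (4-fold) | SPR yes, SCR yes | SPR undetermined, SCR no |
| `<40` | 80 | 40, 80 (2-fold) | SPR yes, SCR no | SPR yes, SCR undetermined |
| `<10` | `<10` | 5, 5 | neither | neither |

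Both branches of the SCR definition require a post-dose titer of at least 40 (4 × 10 = 40 in the second), so a post-dose `<40` can never be a seroconversion. In the fifth row a pre-dose titer below 10, or of 10 or 20, would be a seroconversion and one between 20 and 40 would not. The last row is the routine low result, which the table handles correctly.

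**Step 2: size per affected record.** Let k be the number of post-dose `<40` results among 462 in a group; k is not given in the documents. SPR, and SCR where pre-dose is 10 or less, rises by at most 100k/462 points. Relative to coding such results as 20, the unadjusted group GMT rises by a factor 2^(k/462).

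| k | Points, at most | GMT factor |
|---|---|---|
| 0 | 0 | 1 |
| 1 | 0.22 | 1.0015 |
| 5 | 1.08 | 1.0075 |
| 10 | 2.16 | 1.015 |
| 23 | 4.98 | 1.035 |

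For scale, the CBER limit for SPR (lower 95% limit at least 60%) is first met at 299/462 = 64.7%, where the Clopper-Pearson lower limit is 60.2%; at 298 it is 59.9%.

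**Step 3: between groups.** On the same basis the unadjusted Control/Co-Ad ratio is multiplied by 2^((k_Control − k_Co-Ad)/462), which is 1 when the counts are equal and 1/1.0075 = 0.9925 when Co-Ad has five more.

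A simulation compared the row with the full reading down to 1:10. It took SD 0.6 log10 from the plan and assumed a Control post-dose GMT of 40 to 80, a pre-dose GMT of 15, a pre/post correlation of 0.6, and a share of samples first read at 1:40. These four inputs, including the shares used, have no source in the documents.

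- Equal 5% share in both arms, true ratio 1.05, post-dose GMT 40: the ratio moves from 1.0447 to 1.0434 and the SCR difference from 1.45 to 1.41 points.
- Equal 10% share, true ratio 1.05: the ratio moves by at most 0.0025.
- Equal 10% share, true ratio 1.5: the ratio falls by about 0.02 to 0.03.
- Within a group, a 5% share on post-dose samples raises SPR by 1.6 to 2.5 points and SCR by 1.3 to 2.0. The same share on pre-dose samples lowers SCR by 1.0 to 1.4 points.

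**The case against.** The best answer is that the row may never be used. HI starts at 1:10, which is the cut-off, so the routine low result is `<10` and correctly becomes 5. A `<40` needs a sample first read at a higher dilution, and neither document describes that practice. For the RSV assays, Protocol 10.2 gives neither a start dilution nor a cut-off. This stands, and it is why no expected size can be given.

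Second, one rule applies to both arms and the testing laboratory is blinded to assignment (Protocol 6.3.5), so most of any effect cancels between groups. The SCR comparison is labelled descriptive, and the CBER and CHMP checks carry their own caution about multiplicity (SAP 4.3.1). This also stands.

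Third, SAP 6.2.3.5 ties the conversion to GMT and GMC, so its use for SPR and SCR is inferred. That carries less weight: 6.2.3.4 is worded for all numerical serology results, and no other rule exists for classifying these records.

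A reader might go further and call the table internally inconsistent because low bounds are halved and higher bounds are not. The table does not halve bounds; it assigns half the cut-off, which equals half the bound only when bound and cut-off coincide. A reader might also object to the mirror row, "> value” and value is $<$ assay cut-off cut-off/2", under which `>8` would become 5. Such a result does not fit an HI assay that starts at 1:10, so the documents give no reason to change that row.

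**Conclusion.** The point holds as a conditional one. If an HI result of `<40` occurs, the SAP as written misclassifies it for SPR and, from a pre-dose titer of 10 or less, for SCR. How often this happens is unknown and may be never. The upper limit is 0.22 points per affected post-dose record in a group of 462, and all larger figures above rest on assumed shares.

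Any effect falls mainly on within-group SPR, SCR and MGI and on the CBER and CHMP checks: upward for post-dose records, downward on SCR and MGI for pre-dose records.

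It would be tempting to infer that the row always favours success or threatens the primary non-inferiority conclusions. The documents support neither. The net direction for SCR and MGI depends on which samples are affected, and the GMT ratio shifts little if the affected share is similar in both arms. A larger shift would need a clear imbalance between arms, which nothing in the documents indicates. This is a minor correction, worth making because the rule is explicit and wrong when used.

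**What to change.** In SAP 6.2.3.4:

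- State that SPR and SCR status is derived from the reported bound. A post-dose `< v` with v ≤ 40 is not seroprotected. It is not seroconverted when pre-dose is below 10; for any v, nor is it when the bound rules out a 4-fold rise (pre-dose at least 10 and v ≤ 4 × pre-dose). Where the bound does not determine the status, set it to missing.
- For GMT, MGI and ANCOVA, derive `< value` above the cut-off as value/2, or as cut-off/2 if value/2 is below the cut-off. For HI, `<40` becomes 20, `<20` becomes 10, and `<15` becomes 5 rather than 7.5, in line with 4.2.2.
- List the affected records by group, so that their number and balance are visible.

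The cost is a short text change and minor programming before database lock, with no new data. A few statuses may become missing, and post-dose SPR and SCR may be marginally lower.
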